7. RESEARCH METHODS

7.1. Study Design

Observational, descriptive study of a retrospective cohort of adult patients diagnosed with NVAF in selected Health Maintenance Organization (HMO) of Colombia. These patients will be identified from the drug claim database, whose index date of the study will be the first prescription with any of the oral anticoagulants, that is, they are patients with NVAF for the first time starting a therapy with any of the NOACs between January 1, 2013 and June 30, 2018 and follow up period will be among January 2013 to July 2019, to ensure that the last patients can provide follow-up for one year. Patients will be required to have an NVAF diagnosis before or on the index date and health plan for 6 months pre-index date (baseline period).

Following, it will be verified that the patients meet the inclusion and exclusion criteria of the study. Once patients are selected and with the index date of each patient, they will be followed-up until discontinuation, switch of treatment, death or first event of stroke/ systemic embolism, major bleeding event, death or end of follow-up. Patients who are lost to follow-up, change of HMO and do not have access to the medical record will be considered as missing (Figure 1).

Figure 1. Study Design

[figure not shown]
The information will be analyzed in two moments: (i) the period of the index date, where the baseline information of patients will be collected; (ii) and the follow-up period, during this period the clinical results will be evaluated as well as the continuation of the treatment in the study population and for specific subpopulations.

Those patients who initiated treatment with any oral anticoagulant between January 2013 and June 30, 2018 will be included. This means that patients who start warfarin and NOACs would

be included within this period. Patients who initiate NOACs within the established period and who have been exposed to warfarin before 2013 will also be included.

Only the exposure period will be considered with the initial treatment, even in those patients who were on warfarin treatment before 2013, in the latter, the follow-up will be the treatment initiation with a NOAC in case of change after 2013. Follow-up will be carried out until the patient has a switch of treatment, discontinuation, death, first stroke/ systemic embolism, or major bleeding, or until end of follow-up, June 30, 2019 (Figure 2).

Figure 2. Inclusion of Patients

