7.2.1. Inclusion Criteria

Patients must meet all of the following inclusion criteria to be eligible for inclusion in the study:

- a) Patients with a diagnosis of AF considered according to the following diagnoses as per the ICD I48 codes at some point before or on the index date, without recorded valvular disease;
- b) Patients who have started treatment with apixaban, dabigatran, rivaroxaban and warfarin for the first time during the identification period, understanding as start of drug delivery by insurer, and after the diagnosis of AF between January 1, 2013 to June 30, 2018;
- c) Patients starting apixaban, dabigatran, rivaroxaban from January 1, 2013 to June 30, 2018 in patients previously exposed to warfarin;
- d) Patient had continuous health plan for 6 months pre-index date (baseline period);
- e) Patients older than 18 years old on the index date;
- f) NVAF diagnosis before or on the index date

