7.3.1. Definition of outcome variables

- **OAC escalation:** The dose escalation of the OAC dose will be considered as a dose frequency according to the index dose, as well as the follow-up doses. The proportion of patients experiencing "dose increase", "dose decrease" or "no change" during follow-up with respect to the index dose will be measured, and the time to dose increase or decrease will be calculated.

C
C
I

C
C
I

- **Switch of treatment:** A switch among anticoagulants will be defined as a prescription filled for non-index anticoagulants within +/- 30 days after the date of discontinuation.
- **Persistence:** Persistence will be defined as the time under OAC therapy, calculated as the time in days from the index date to the date of discontinuation or change to treatment. As previously stated, discontinuation will be defined as a change of treatment, that is, to another OAC, or when there is no evidence of a prescription for 60 days from the last supply delivered, whichever comes first.

Therefore, if a patient does not receive his next prescription for the OAC therapy within 60 days after the end of the previous prescription, it will be considered that he discontinued therapy, and the date of the last prescription will be considered as the final date of persistence.

Persistence with OAC therapy will be considered during the period of individual patient follow-up. Patients will be censored at the end of their follow-up period.

- **Major bleeding:** Patients presenting any of the following diagnoses during the follow-up period:

ICD-10	Description
I60	Subarachnoid haemorrhage
I61	Intracerebral haemorrhage
I62	Other nontraumatic intracranial haemorrhage
I690	Sequelae of subarachnoid haemorrhage
I691	Sequelae of intracerebral haemorrhage
I692	Sequelae of other nontraumatic intracranial haemorrhage
S064	Epidural haemorrhage
S065	Traumatic subdural haemorrhage
S066	Traumatic subarachnoid haemorrhage
I850	Oesophageal varices with bleeding
K250	Acute with haemorrhage

Apixaban

B0661148- NON-INTERVENTIONAL STUDY PROTOCOL

Final, 10 October 2019

ICD-10	Description
K252	Acute with both haemorrhage and perforation
K254	Chronic or unspecified with haemorrhage
K256	Chronic or unspecified with both haemorrhage and perforation
K260	Acute with haemorrhage
K262	Acute with both haemorrhage and perforation
K264	Chronic or unspecified with haemorrhage
K266	Chronic or unspecified with both haemorrhage and perforation
K270	Acute with haemorrhage

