7.7 Data Analysis

This type of analysis is descriptive and explanatory, as it depends largely on the sample size. Continuous variables will be presented as means, standard deviation or other measures of central tendency or position, while categorical variables will be presented as frequencies and percentages.

Regarding bivariate analyses of continuous variables with normal behavior, the Student's t test will be performed. In case of presenting non-normal behavior, the Mann-Withney test will be used. For variables that are continuous with several categories, analysis of variance (ANOVA) will be assessed. In the event of presenting a non-normal behavior, the multivariate analysis of

variance (MANOVA) test will be carried out. For categorical variables, the X² test will be used.

Exploratory analyses based on sample size:

The cumulative incidence of clinical outcomes (Stroke/ systemic embolism and major bleeding) will be calculated throughout the study period, from which the incidence or survival curves will be derived using the Kaplan Meier method. Incidence of events will be explored in clinically relevant subgroups based on sample size.

For the execution of the analysis, CCI and change of treatment, and missing treatments are considered as censures. Treatment comparison will be not conducted.

A similar analysis will be performed for the group of patients who have not presented stroke/ systemic embolism or major bleeding events to estimate the time for CCI change of treatment.

In the independent variables, the significance will be analyzed, as a level of statistical significance p < 0.05.

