7.7.1 Missing Data Management

There will be no imputation or replacement of missing data. All analyses will be conducted on observed cases.

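### The visible 60-day rule counts a patient who leaves the HMO while on treatment as discontinued, and no censoring date is set for leavers

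*Combined protocol and SAP*

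**What the plan says.** Five pieces of visible text bear on a patient who leaves.

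- **Label.** Section 7.1: "Patients who are lost to follow-up, change of HMO and do not have access to the medical record will be considered as missing". No date is attached.
- **End of follow-up.** Section 7.1: "they will be followed-up until discontinuation, switch of treatment, death or first event of stroke/ systemic embolism, major bleeding event, death or end of follow-up". Later in the same section a second list closes with "or until end of follow-up, June 30, 2019". Section 7.2 has a third list. None of them names HMO exit or loss to follow-up. Section 7.2.1 requires health-plan membership only for the six months before the index date.
- **Discontinuation.** Section 7.3.1 counts a change of OAC, or "when there is no evidence of a prescription for 60 days from the last supply delivered, whichever comes first". It then repeats the gap rule ("if a patient does not receive his next prescription for the OAC therapy within 60 days after the end of the previous prescription") and ends persistence at the last prescription. It adds that patients are censored when their own follow-up ends.
- **Censoring of clinical outcomes.** Section 7.7, after the Kaplan-Meier paragraph and in a sentence whose first item is blacked out, says that "missing treatments are considered as censures".
- **Missing data.** Section 7.7.1 rules out imputation and says "All analyses will be conducted on observed cases".

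Persistence is part of the second primary objective (Section 6) and is taken from the claims database (Table 1).

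**The concern.** A retrospective claims cohort with follow-up from 2013 to mid-2019 will lose some patients to other insurers. When that happens the OAC fills may stop appearing although treatment goes on. The data then look the same as a true discontinuation unless enrolment is checked, and the visible gap rule does not check it. Every such patient adds a false event to the persistence curve, so persistence is understated. If exit rates differ between the four OAC cohorts, the described persistence will also differ between them for reasons that have nothing to do with treatment.

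There is a second, weaker worry. The label missing, together with the observed-case rule, could lead a programmer to exclude leavers altogether. That would select the cohort on something that happens after the index date.

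Section 7.9 notes that hospital stays can hide continued therapy, but it does not mention plan exit, which hides it in the same way and for longer.

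**Working it through.** **1. Trace one patient through the text.** Take a patient who is on treatment, changes HMO, and has no further fills in the claims data.

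- The lists in Sections 7.1 and 7.2 do not end follow-up at exit.
- Sixty days after the last supply runs out, the Section 7.3.1 gap rule is met. The patient is a discontinuation, dated to the last prescription, which falls on or before the exit.
- The censoring sentence in Section 7.3.1 does not prevent this. It censors at the end of individual follow-up, which is undefined for a leaver. Even if exit were that end, the backdated discontinuation would come no later than it.
- The censoring of missing treatments in Section 7.7 does not clearly help either. The term is undefined, the sentence follows the clinical-outcome analysis, and for persistence the supply gap is itself the event.

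**2. Size of the effect on persistence.** The plan states no persistence, exit or discontinuation figure, so there is nothing to reproduce. All inputs are assumptions: independent exponential times, discontinuation hazard 0.30 per year, exit hazard l = 0.05 or 0.10 per year.

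- Leavers censored at exit: S(t) = exp(−0.30t).
- Leavers counted as discontinued: S(t) = exp(−(0.30 + l)t).

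| t | Censored at exit | Counted, l = 0.05 | Counted, l = 0.10 |
|---|---|---|---|
| 1 year | exp(−0.30) = 74.1% | exp(−0.35) = 70.5% | exp(−0.40) = 67.0% |
| 3 years | exp(−0.90) = 40.7% | exp(−1.05) = 35.0% | exp(−1.20) = 30.1% |

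The false discontinuation is placed at the exit date here. Dating it to the last prescription moves it no later.

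**3. Other assumed rates.** With true 12-month persistence of 70% and 5%, 10% or 20% of patients leaving per year, counting leavers as discontinued gives 0.70 × 0.95 = 66.5%, 0.70 × 0.90 = 63.0% and 0.70 × 0.80 = 56.0%. With true persistence of 50% the values are 47.5%, 45.0% and 40.0%.

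**4. If leavers were excluded instead.** Patients who discontinue first cannot leave while on treatment. On the step 2 inputs the share that leaves by time t is therefore l/(0.30 + l) × (1 − exp(−(0.30 + l)t)):

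- year 1: 0.05/0.35 × (1 − 0.705) = 4.2%, and 0.10/0.40 × (1 − 0.670) = 8.2%;
- year 3: 0.05/0.35 × (1 − 0.350) = 9.3%, and 0.10/0.40 × (1 − 0.301) = 17.5%.

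A simulation of 2,000,000 patients, with true 12-month persistence of 70% and administrative follow-up uniform from 1 to 6.5 years, gives 67.7%, 65.3% and 60.2% at 5%, 10% and 20% exit per year when leavers are dropped. Exclusion would also bias persistence downward. For clinical outcomes the effect is smaller: with an assumed event rate of 2% per year and 60% one-year persistence, dropping leavers moves one-year cumulative incidence from 2.0% to about 2.1–2.7% over the same exit rates.

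**The case against.** The strongest reply is that much of this is ambiguity rather than a stated error. A reader might infer that leavers are removed from the study, or that the plan lays down three contradictory rules for the same patient. The documents do not support either reading.

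- Section 7.1 only attaches a label. In a survival analysis, using observed cases is compatible with using observed time up to loss.
- The missing treatments of Section 7.7 may be meant to cover these patients, who would then be censored, and part of that sentence is blacked out.
- The *and* in Section 7.1 may confine the label to patients whose record cannot be reached. That would fit Section 7.2, which limits the study to patients with accessible records.
- Figure 1, which the sentence cites, is not shown. Redacted items also precede the persistence definition, which refers back to an earlier statement on discontinuation.

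All of this stands, and it rules out saying that leavers are dropped. It does not answer the point about persistence. The 60-day rule is set out in full in the visible text, dates the event back to the last prescription and carries no enrolment condition. The narrow reading of *and* makes matters no better: leavers with an accessible record then have no rule except the gap rule. A patient who moves to an HMO whose fills still reach the database is not affected.

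**Conclusion.** The point holds as follows. In the visible text, HMO exit and loss to follow-up are not ends of follow-up and have no censoring date. As written, the 60-day rule turns a patient who leaves on treatment, with no further fills in the claims data, into a discontinuation. That biases persistence downward by about 4 to 7 percentage points at 12 months and about 6 to 11 points at 3 years, on assumed hazards of 0.30 per year for discontinuation and 0.05 to 0.10 for exit. The direction follows from the rule. The size depends on an exit rate that the documents do not give, and on fills being lost from view after exit.

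Exclusion of leavers is a risk that the wording invites, not something the plan states. The clinical-event curves are the lesser concern. The text should be changed, because the affected quantity belongs to a primary objective and the correction is small.

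**What to change.** In Sections 7.1, 7.3.1 and 7.7, and in the list in Section 7.2:

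1. Name HMO exit and loss to follow-up as ends of follow-up.
2. Keep these patients in the persistence and time-to-event analyses, censored at the exit date or, if none is held, at the last available data.
3. Count a 60-day gap as discontinuation only if the patient was still enrolled throughout the gap.
4. Reserve the label missing for patients without an accessible record, and say what missing treatments means in Section 7.7.
5. Report the number of leavers in each cohort.

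The cost is a few sentences plus enrolment or last-record dates. Section 7.4.1 lists insurance data in the claims database but does not say that exit dates are held, so this needs checking first. Censoring is the standard choice, but it assumes that exit is unrelated to outcome. The plan should say so, and Section 7.9 should list plan exit as a limitation.

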2. ABSTRACT

Study title: Patient characteristics, treatment patterns and incidence of events (discontinuation, persistence, key primary clinical outcomes) in NVAF patients initiating OAC therapy in Colombia				
Protocol number	B0661148	Phase	4	Type
Condition/Disease	Non-valvular atrial fibrillation (NVAF)			
Number of patients	The total population of patients treated with OAC between January 1, 2013 and June 30, 2018 was analyzed in the claim dabtabase. For the purpose of the study, it contains the information of 7,500 patients, once they were verified that they met the inclusion criteria of the study.	Duration of the patients in the study	Follow-up will be performed until the patient presents a switch, discontinuation, death, event of stroke / systemic embolism or major bleeding, or until June 30, 2019.	
Country participants	Colombia	Duration of the study	8 months	
Rational and background: Non-valvular atrial fibrillation (NVAF) is an acute or chronic heart disorder that is associated with an increase in the mortality rate, strokes and other thromboembolic events (1). This is further increased by individual conditions of patients, such as hypertension, abnormal renal or hepatic function, stroke, history of or predisposition to bleeding, people over 65, among others. (2)				
One of the standard treatments for management of these patients is usually vitamin K antagonists (VKA, for example, warfarin); in the analysis of net clinical benefits of this therapy it is suggested that the effect of VKA is even more positive in patients with a high score on the HAS-BLED (hypertension, abnormal renal/liver function, stroke, bleeding history or predisposition, labile International Normalized Ratio, elderly, drugs/alcohol concomitantly) scale. (3) Another therapeutic alternative is the new oral anticoagulants (NOACs) — dabigatran, rivaroxaban and apixaban —, which according to evidence have advantages in efficacy and safety compared to warfarin (4) and even when the risk of bleeding and stroke are high, the net clinical benefit appears to be greater when compared to warfarin. (5) Likewise, there is a lower prevalence of intracranial hemorrhage and its different subtypes of patients being treated with new oral anticoagulants when compared to warfarin. (6)				

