The cumulative incidence of clinical outcomes (stroke/ systemic embolism and major bleeding) will be calculated throughout the study period, from which the incidence or survival curves will be derived using the Kaplan Meier method. Incidence of events will be explored in clinically relevant subgroups based on sample size.

A similar analysis will be performed for the group of patients who have not presented stroke/ systemic embolism or major bleeding events to estimate the time for discontinuation events and change of treatment.

In the independent variables, the significance will be analyzed, as a level of statistical significance $p < 0.05$.

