7.2. Setting

The study will be conducted with the Audifarma patient cohort that meets the inclusion and exclusion criteria between the periods from January 2013 to June 30, 2018. The follow up period will be among January 2013 to July 2019, to ensure that the last patients can provide follow-up for one year.

This study will include the entire population in which medical records can be accessed. This will depend on the authorization of the HMOs for review of medical records. Participating patients will be followed-up until the patient has a stroke/systemic embolism, major bleeding, discontinuation, change of treatment or until the data collection period is completed.

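### All follow-up ends at the first stroke/embolism or major bleed, so persistence is potentially informatively censored and each clinical outcome truncates the other

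*Combined protocol and SAP*

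**What the plan says.** The Abstract and Sections 7.1 and 7.2 share one end-of-follow-up rule. Section 7.1: "Follow-up will be carried out until the patient has a switch of treatment, discontinuation, death, first stroke/ systemic embolism, or major bleeding", or June 30, 2019. Section 7.2: "Participating patients will be followed-up until the patient has a stroke/systemic embolism, major bleeding, discontinuation, change of treatment" or the end of data collection; death is not listed there. The Abstract: "Follow-up will be performed until the patient presents a switch, discontinuation, death, event of stroke / systemic embolism or major bleeding". No visible text continues observation of one outcome after another has occurred.

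Section 7.3.1 considers persistence only within individual follow-up and adds: "Patients will be censored at the end of their follow-up period". Discontinuation is a change of OAC or a 60-day gap in supply, and after a gap "the date of the last prescription will be considered as the final date of persistence".

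The exploratory analysis adds a restriction. The Abstract says "A similar analysis will be performed for the group of patients who have not presented stroke/ systemic embolism or major bleeding events", with time to discontinuation and to change of treatment as the endpoints. Section 7.7 repeats this with part of the text redacted. The estimator is Kaplan-Meier. The visible censoring list in Section 7.7 names change of treatment and missing treatments, after a redacted item. No competing-risk method or sensitivity analysis for censoring at a clinical event is described.

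**The concern.** Kaplan-Meier assumes that patients censored at a given time would have gone on to stop treatment at the same rate as those still observed. A bleed or stroke is a plausible reason to stop or change an anticoagulant, and Table 1 itself lists adverse events and effectiveness among the causes of change. Censoring persistence at such an event may therefore remove patients just when their chance of stopping rises. The major-bleeding code list is broad (it includes unspecified haematuria, postmenopausal bleeding and haemarthrosis), so a fairly minor coded bleed closes every clock.

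The event-free restriction is a separate problem. Whether a patient belongs to that group is known only after follow-up has run. Excluding those with an event preferentially removes patients who stayed on treatment long enough to have one.

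Persistence belongs to a primary objective (Section 6). The stroke/embolism and bleeding curves are exploratory, but each also loses the experience of patients who have already had the other event.

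**Working it through.** **Inputs.** The documents give no rate for discontinuation, events or stopping after an event, so there is no plan figure to reproduce. Every rate below is an assumption. From the documents: entry January 2013 to June 2018 and end June 30, 2019, so potential follow-up is 1 to 6.5 years. All models use constant, independent hazards: d = discontinuation for other reasons, b = event rate, q = share stopping because of the event.

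**1. Persistence censored at the event.** The event-censored curve estimates exp(-dt). Following patients through the event gives approximately exp(-(d + qb)t). With d = 0.30/year, q = 0.5 and bleeding as the event:
- 12 months, censored: exp(-0.30) = 74.1%.
- 12 months, followed through: b = 0.04 gives exp(-0.32) = 72.6%; b = 0.10 gives exp(-0.35) = 70.5%.
- 3 years, censored: exp(-0.90) = 40.7%. Followed through: exp(-0.96) = 38.3% and exp(-1.05) = 35.0%.
- q = 0: the two curves coincide and the difference is zero.

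A stricter form, in which only the first event can cause stopping, is exp(-dt) × [1 - q(1 - exp(-bt))]. It gives 72.6% and 70.6% at 12 months. Over wider assumptions (d = 0.2-0.7, b = 0.03-0.12), this form puts the 1-year overstatement at 0 for q = 0, 0.4-2.8 points for q = 0.3, 0.9-5.6 for q = 0.6 and 1.3-8.3 for q = 0.9.

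**2. Persistence restricted to event-free patients.** With h = d + b and common administrative censoring at C, the estimate is [(d/h)(exp(-ht) - exp(-hC)) + exp(-hC)] / [(d/h)(1 - exp(-hC)) + exp(-hC)]. Take d = 0.4, b = 0.06, C = 3, t = 1:
- d/h = 0.8696, exp(-0.46) = 0.6313, exp(-1.38) = 0.2516.
- Numerator 0.5818, denominator 0.9024, ratio 64.5%.
- Followed through the event with q = 0.6: exp(-0.4) × [1 - 0.6 × (1 - exp(-0.06))] = 64.7%.
- Censored at the event: exp(-0.4) = 67.0%.

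So for the same patients, event censoring is 2.3 points too high and the event-free restriction 0.2 points too low. Over the wider grid the event-free error at 1 year runs from -5.2 to +4.2 points. It is negative in every q = 0 and q = 0.3 scenario, mixed at q = 0.6 and positive at q = 0.9. A simulation of 2,000,000 patients, with follow-up uniform on 1-6.5 years, gave 64.7% (true), 67.1% (censored) and 64.4% (event-free); about 10% of patients were removed by the restriction.

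**3. Stroke person-time lost after a bleed.** On-treatment person-time over T years at total exit rate r is (1 - exp(-rT))/r. The stated rule has r = d + b. Following past the bleed, with half of bleeders stopping, has r = d + 0.5b. With d = 0.30 and T = 3.5 (assumed):
- b = 0.03: 2.076 against 2.121 years, a loss of 2.1%.
- b = 0.10: 1.884 against 2.018 years, a loss of 6.7%.

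By simulation, with stroke at 0.015/year and wider inputs (b = 0.03-0.12, d = 0.2-0.4, q = 0.3-0.6), about 2-13% of on-treatment first strokes follow a bleed. About 2% of bleeds follow a stroke.

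**4. Order of dates.** Suppose a patient fills a prescription, bleeds before the next fill and never refills. Section 7.3.1 dates the end of persistence at the last prescription, before the bleed; Section 7.1 ends follow-up at whichever comes first. Read literally, the discontinuation counts and the bleed falls after follow-up. Read the other way, the bleed counts and the discontinuation is censored. The documents do not say which prevails.

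**The case against.** A reader might infer that a discontinuation after a bleed is never counted. The documents do not support that: under the backdating rule some such discontinuations are dated before the bleed and, read literally, are counted.

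A reader might also infer that reported persistence must be too high. That holds for the event-censored curve only if events raise stopping, and the documents give no rate for this. For the event-free analysis the error can go either way.

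A person-time loss of 4-12% is tempting as well, but it assumes that no bleeder stops because of the bleed. Applying the 50% used for persistence roughly halves it.

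The remaining objections carry some weight. The clinical outcomes are exploratory and descriptive, confined to patients persistent on therapy, and Section 7.7 rules out treatment comparison, so their mutual truncation matters less. Codes I60-I62 are listed under both major bleeding and haemorrhagic stroke, so those events count for both on one date. Part of the censoring text is redacted and the design figures are not shown, so the point rests on the visible text. None of this removes the common stopping rule, which is stated in three places, or the censoring of persistence at its end.

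**Conclusion.** The point stands as an avoidable design weakness that should be corrected. The stated rules make persistence potentially informatively censored, and a second analysis conditions on future events. Neither the direction nor the size of the error in the reported persistence can be fixed from the documents. For event-censored Kaplan-Meier it is zero if stopping is unrelated to the event, and 1.5 to 3.6 points at 12 months (74.1% against 72.6-70.5%) under the illustrative rates. For the event-free analysis it is of either sign. The loss to the stroke outcome is about 2-7% of on-treatment person-time if half of bleeders stop. All figures assume constant and independent hazards. If frailty or another factor drives both events and stopping, the size would differ.

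**What to change.** 1. Estimate persistence from claims in all patients, to discontinuation or switch. Let death, disenrolment and June 30, 2019 end follow-up, but not a stroke/embolism or bleed. Remove the event-free restriction from the Abstract and Section 7.7.
2. Follow stroke/embolism and major bleeding each to its own first event on treatment, regardless of an earlier event of the other type. Amend the Abstract and Sections 7.1, 7.2 and 7.3.1 to match, and align the listing of death.
3. State which date takes precedence when the backdated discontinuation date falls before a clinical event.
4. Reconcile exclusion g in Section 7.2.2 (more than one OAC during follow-up) with counting switches. If follow-up runs past an event, patients who switch afterwards would otherwise meet that exclusion.

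**Cost.** Mostly wording. Section 7.4.1 says the claims database holds all prescriptions in time order, so persistence needs no new data. Abstractors would read further only in the minority with an event. Section 7.9 says hospitalizations are not captured, so some supply gaps around a stroke or bleed may be misclassified as discontinuation; this should be added to the limitations.
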